### 5.2. Exclusion criteria

Patients under 18 years of age or over 60 years of age;

Dementia who could not cooperate, or affecting the judgment of curative effect;

Women who were pregnant, breastfeeding or who might become pregnant during the study and who were not using effective contraceptives;

Patients suffering from tuberculosis, tumor and other organic lesions;

Known alcohol and drug dependence;

To determine the patients who were not suitable for this clinical observation;

People with coma, bleeding tendency and allergic constitution were excluded;

Treatments such as hormones, diuretics, hypertonic dehydrating agents, thrombolysis, anti-coagulation, and fibrillation that might affect the results of the study;

Staff directly involved in the study;

Other circumstances that other physicians or researchers had judged inappropriate for participating in the clinical trial

---

---

### **5.3. Case withdrawal criteria**

Discontinuation of *Bacillus subtilis* spore due to side effect determined by the investigator;  
Discontinuation of *Bacillus subtilis* spore due to other reasons (including voluntary withdrawal);  
Unable to cooperate;  
For reasons other than research-related, the investigator did not consider it appropriate to continue the clinical trial.

### **5.4. Management of cases of loss**

Definition of cases of loss: all subjects who had completed the informed consent form and were screened for entry into the study, at any time and for any reason withdrawal, as long as the subjects did not complete the observation period specified in the protocol, was called cases of loss, including the following conditions:

A serious side effect occurred in the subject and, in the judgment of the physician, the case should be discontinued.

During the study, the subjects' original condition worsened or other symptoms occurred during the study that affected the observation of the study, according to the doctors decided that the clinical trial should be stopped.

Significant deviations occurred during the implementation of the clinical trial protocol, making it difficult to evaluate the vaccine effect.

Subjects were unwilling to continue the clinical trial.

Treatment of cases of loss: contacted subjects with reasons, recorded the time of last observation, and completed the assessment items that could be completed. For patients who withdrew from the study due to allergy or other side effect and failure to respond to treatment, the investigator should take appropriate treatment measures according to the actual situation of the subjects. The researchers should properly preserved the relevant experimental data of the cases of loss, not only for filing, but also for carrying out the complete analysis set statistics.

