### 10.2.2. Statistical description

Whether it conformed to normal distribution:

Modified the statistical method or carried out data conversion in case of inconsistency;

---

With and without outliers: Conducted statistical and professional analysis to decide whether to choose or not;

Missing value processing of primary efficacy index data: when a certain primary efficacy data of individual subjects was missing, the data would be collected from the statistics and professional standpoint. If the shedding case was missing, transferred with the previous measurement data; For missing data only one measurement index, all data was used to fill the gap.

The proportion of shedding cases: If it exceeded 20%, it should be analyzed and explained;

Descriptive statistical analysis: Indicated mean, standard deviation, maximum, minimum, median, confidence interval, and frequency (composition ratio), etc.

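### Sections 5.3 and 5.4 let side effects, stopping the product and significant deviations end a subject's observation, and nothing requires the remaining D7 to D28 visits

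*Combined protocol and SAP*

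**What the plan says.** All references are to the combined protocol and SAP.

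- **Section 5.3 (withdrawal criteria).** The first criterion is discontinuing the "spore due to side effect determined by the investigator". The second is discontinuing it for any other reason. Stopping the product is thus itself a ground for withdrawing the case.
- **Section 5.4 (definition of loss).** Withdrawals at any time and for any reason count: "as long as the subjects did not complete the observation period specified in the protocol, was called cases of loss".
- **Section 5.4 (listed conditions).** Besides unwillingness to continue, these are:
  - "A serious side effect occurred in the subject and, in the judgment of the physician, the case should be discontinued";
  - "the subjects' original condition worsened or other symptoms occurred during the study that affected the observation of the study", again on the doctors' decision;
  - "Significant deviations occurred during the implementation of the clinical trial protocol, making it difficult to evaluate the vaccine effect".
- **Section 5.4 (after loss).** Sites ask for the reasons, and the text adds "recorded the time of last observation, and completed the assessment items that could be completed". Data on lost cases are kept for the full analysis set.
- **Section 10.2.2 (missing primary data).** "If the shedding case was missing, transferred with the previous measurement data".
- **Section 7.4.** All clinical examinations, trial indicators and routine laboratory tests are scheduled for D0, D7, D14, D21 and D28.
- **Section 8.1.** Side effects count up to the last follow-up.
- **Section 11.1.** Sites are to keep loss within 20%.

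**The concern.** Leaving the product and leaving the study are different events, and these sections do not separate them. Subjects who have a side effect, get worse or deviate importantly are the ones whose later data matter most for safety. Their antibody response may also differ from that of subjects who finish. If their visits stop, three things follow:

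- Later laboratory tests and new events may go unseen, because the reporting window in section 8.1 in practice closes with the subject's last follow-up.
- The primary antibody result rests on a carried-forward early value, or on those who finished. The per-protocol set in section 10.2.1 requires all evaluations to be complete.
- A subject lost before any efficacy evaluation falls outside the ITT population as section 10.2.1 defines it.

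Safety and immunogenicity are the trial's whole purpose, and a missed blood sample cannot be taken afterwards.

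**Working it through.** **Step 1: does any section keep these subjects on the visit schedule?**

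| Section | What it provides | What it leaves open |
|---|---|---|
| 4.1 | Follow-up to normal of abnormalities or side effects present when the study ends | Scheduled visits before that point |
| 5.4 | Feasible assessments, retained data, treatment where needed | Whether the remaining visits take place |
| 7.4 | Immediate follow-up when a side effect is found | Duration, and any rule for withdrawn subjects |
| 8.5 | A form with the course and outcome of a serious event | New events, routine laboratory tests, antibody samples |
| 11.1 | Active effort to limit dropout | Withdrawal that the investigator decides |

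None requires the later scheduled laboratory tests or antibody samples. A subject whose observation ends after D7 misses D14, D21 and D28, which is 3 of the 4 follow-up visits.

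**Step 2: inputs for the size.** The documents give no sample size, response rate or event rate, and they do not define an antibody responder. There is no figure of the plan's own to reproduce. The 20% loss limit (sections 10.2.2 and 11.1) is the only input on loss. Every rate below is an assumption.

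**Step 3: completer-only (per-protocol) response rate.** Let d be the share lost, r the response rate in completers and q the rate in lost subjects. The true rate is (1 − d)r + dq, so the completer rate is too high by d(r − q).

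| d | r − q = 0 | r − q = 20 points | r − q = 40 points |
|---|---|---|---|
| 20% | 0 | 0.20 × 20 = 4 | 0.20 × 40 = 8 |
| 10% | 0 | 0.10 × 20 = 2 | 0.10 × 40 = 4 |
| 5% | 0 | 0.05 × 20 = 1 | 0.05 × 40 = 2 |

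The 20% limit covers all loss, including refusal. If half of it were investigator-driven, the part that the fix could address is the 10% row.

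**Step 4: limits with no assumption about q.** The true rate lies between (1 − d)r and (1 − d)r + d. With d = 0.20 and r = 0.70, that is 0.80 × 0.70 = 56% to 56% + 20% = 76%. The completer figure of 70% could therefore be too high by 14 points or too low by 6.

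**Step 5: carry-forward.** Suppose the response rises linearly to D28 and lost subjects respond like the others. If v is the day of the last value, the estimated mean rise is (1 − d) + d·v/28 of the true one. At d = 0.20:

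- v = 0: 0.80 + 0 = 80%
- v = 7: 0.80 + 0.05 = 85%
- v = 14: 0.80 + 0.10 = 90%
- v = 21: 0.80 + 0.15 = 95%

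This error is downward, opposite to that in step 3.

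**Step 6: safety.** Let later events occur in 2% of retained subjects and in a share p of lost subjects, and suppose those in lost subjects all go unseen. The missed share of later events is dp / [(1 − d) × 0.02 + dp]. At d = 0.20:

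- p = 2%: 0.004 / 0.020 = 20%
- p = 10%: 0.020 / 0.036 = 56%
- p = 30%: 0.060 / 0.076 = 79%

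At d = 0.05 the shares are 5%, 21% and 44%. These are upper figures, because the safeguards in step 1 would catch some events.

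**The case against.** The strongest reply is that the text is milder than it looks.

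- **Nothing tells sites to stop collecting.** A reader might infer that it does, but section 5.4 asks for the assessments that can still be done and keeps the data. This stands. The defect is that the remaining visits are not required, not that they are forbidden.
- **Loss is not automatic.** A reader might infer that every serious side effect or deviation ends observation. The text requires a physician's judgment for the first and a significant deviation that hampers evaluation for the second. This also stands.
- **Loss is defined by incomplete observation.** On that wording, a subject who stops the product but attends to D28 is not lost. This is fair, but section 5.3 lists stopping under case withdrawal and never says that visits go on.
- **There may be nothing to stop.** Sections 4.1 and 4.2 describe one dose taken once, while Summary item 3 and section 6.3 say once a day. Under the first reading the stopping criterion has little content. The conditions in section 5.4 can still end observation after the only dose.
- **Safeguards exist, and carry-forward covers primary efficacy data only.** Both are true. The safeguards reduce the safety gap but do not replace scheduled tests.

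**Conclusion.** The concern holds in a limited form. The stated rules allow observation to end for reasons related to outcome, and no section requires the later scheduled safety and antibody assessments. This can weaken safety ascertainment and may bias the immunogenicity result. It should be corrected before enrolment.

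A reader might infer a known upward bias, for example 4 to 8 points. The documents do not support that. Such a figure needs all loss at the 20% limit, a completer-only estimate and an assumed gap of 20 to 40 points. With a gap of 0 to 40 points the range is 0 to 8 points, and lower if only part of the loss is investigator-driven. The carry-forward rule can pull the estimate the other way. Neither size nor direction is settled. The safety gap does not depend on any difference in antibody response.

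**What to change.** In sections 5.3 and 5.4:

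1. Define stopping the product separately from leaving the study.
2. State that stopping the product, a side effect or a protocol deviation does not by itself end follow-up.
3. Ask subjects who took a dose to continue the D7, D14, D21 and D28 safety and antibody assessments unless they withdraw consent for follow-up, die, are lost to contact, or cannot attend or cooperate.
4. Handle deviations through the analysis-set definitions, not by ending observation.
5. Reconcile sections 4.1 and 4.2 with Summary item 3 and section 6.3, so that discontinuation has a clear meaning.

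Decisions on stopping the product and on clinical care stay with the investigator. The cost is a change of wording and some extra effort to retain subjects at visits already scheduled.

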## **6. Test subject**

### **6.1. Test subject**

Generic name: *Bacillus subtilis* spore

Specifications: Tablets

Batch number:

Storage: under 4°C, sealed in the dark place

Production unit:

---

### **6.2. Vaccine packaging**

---

Single 1 capsule, individually packed.

### **6.3. Administration**

Test group: Oral approach, 1 capsule B. subtilis spore once a day. No other medication.

Start in the morning on an empty stomach.

Control group: Oral approach, 1 simulated tablet once a day. No other medication.

Start in the morning on an empty stomach.

### **6.4. Vaccine management**

Preservation conditions of the study vaccine: under 23°C, the vaccine was kept in a closed and dark place.

The quality of the clinical trial vaccine, including the control tablet, should be checked regularly to meet the storage conditions. The test center would be reserved and managed by special personnel.

The use of the study vaccine was the responsibility of the investigator, who should not transfer the study vaccine to any non-clinical trial participant.

When distributing vaccine to subjects, researchers should fill in the registration form of vaccine distribution in a timely and accurate manner.

After the end of the trial, the remaining vaccine would be collected for unified disposal.

### **6.5. Combination of medicines and prohibited medicines**

Other anti-influenza medicines should not be used during the trial.

---

## 7. Clinical efficacy indexes and safety evaluation criteria

### 7.1. Main efficacy indicators

Immunogenicity of vaccines

### 7.2. Other efficacy indicators

Safety of vaccines

Mortality

#### 7.2.1 Immunogenicity of vaccines:

To test the immunogenicity induced by oral vaccine

Compared vaccine-induced immunogenicity with natural infection immunogenicity

#### 7.2.2 Safety of vaccines

Observed whether mild to moderate symptoms such as fever and chills appeared after taking the vaccine;

Observed whether there were severe symptoms such as coagulation dysfunction and allergy after taking the vaccine;

Observed whether there were serious symptoms such as disability after taking the vaccine.

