This product was bacillus subtilis spore vaccine. Various types of vaccines such as mRNA, adenovirus and inactivated virus via injection route were developed to prevent the infection of SARS-CoV-2. Although some of them have already been approved to against the COVID-19 pandemics, various drawbacks including severe side effects and instability in storage may hinder their applications. *Bacillus subtilis* (*B. subtilis*) is a generally recognized as safe (GRAS) and endotoxin-free gram-positive bacterium, which has been extensively employed as a host for expression of recombinant proteins. Its dormant spores are extraordinarily resistance to harsh environment conditions in gastrointestinal tract. This feature makes it an ideal candidate for oral administration to resist the environment. In this study, an engineered *B. subtilis* spore expressing the spike protein receptor binding domain (sRBD) of the SARS-CoV-2 on the surface was developed, and the result proved that it successfully increased the neutralizing antibody against sRBD in unvaccinated mice and human individuals after oral administration. These findings may enable the use of *B. subtilis* spore as oral vaccine against COVID-19 in the future.

The oral vaccine presents antigen through the gastrointestinal mucosa and could produce an immune response similar to that of conventional injection through different immune pathways. With the development of medicine and molecular biology technology, great progress had been made in the study of oral vaccine in the presentation of mucosal antigen, which could effectively induce immune response and immune tolerance in the body. The toxicity of the vaccine was very low, and the LD50 could not be measured by oral or peritoneal route. According to the toxicity grading standard, it was basically non-toxic. Long-term toxicity, specific toxicity and reproductive toxicity studies did not show any biological damage. Experimental data showed that the vaccine was extremely safe and well tolerated by patients.

---

---

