## 7.3. Security indicators

General data: physical examination

Laboratory examination: Routine blood examination (including erythrocyte count, leukocyte count, hemoglobin, platelet count, proportion of monocytes, lymphocytes and neutrophils), urine routine (erythrocyte, leukocyte, urine protein), liver and kidney function (including ALT, AST, TBIL, BUN, Cr).

Symptoms accompanying any discomfort were recorded by the investigator

a) No: No symptoms

- b) Mild: Weak symptoms sometimes appeared
- c) Moderate: persistent but not noticeable after distraction
- d) Severe: Persisting no matter when

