#### **7.4. Follow-up examination**

The first examination was performed on the day of study start (D0). Follow-up was conducted every 7 days (i.e. D7, D14, D21, and D28) for all clinical examinations, all indicators of the trial, and routine laboratory examinations.

Side effect should be recorded during routine daily clinical examinations. If any side effect was found, follow up immediately and informed the researcher.

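### No gastrointestinal symptom is named for observation of an oral product said to act through the gut mucosa, and no uniform symptom question, symptom diary or D0 symptom record is specified

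*Combined protocol and SAP*

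**What the plan says.** All references are to the combined protocol and SAP.

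- **Site of action (1. Introduction).** The spores are chosen because "Its dormant spores are extraordinarily resistance to harsh environment conditions in gastrointestinal tract", and "The oral vaccine presents antigen through the gastrointestinal mucosa".
- **Named reactions (7.2.2).** There are three lines. The first reads "Observed whether mild to moderate symptoms such as fever and chills appeared after taking the vaccine". The second concerns severe reactions and gives two examples, coagulation dysfunction and allergy. The third concerns serious reactions and gives one example, disability.
- **General symptom item (7.3).** "Symptoms accompanying any discomfort were recorded by the investigator", on four levels from no symptoms to severe. No body system is named.
- **Timing (7.4).** Examinations take place at D0 and then at D7, D14, D21 and D28. The same section adds: "Side effect should be recorded during routine daily clinical examinations".
- **D0 content (7.4.1).** Consent, eligibility, medical and medication history, physical examination and laboratory tests are listed. The symptom grading of 7.3 is not.
- **Scope of side effects (8.1).** Every adverse medical event from consent and enrolment to last follow-up counts, whatever its cause.
- **Diary (11.1).** The card is described as holding the subject's vaccination status only.
- **Analysis (10.2.3 and 10.2.6).** Side effects are described and counted. A before-and-after comparison is specified for laboratory values, and none for symptoms.

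**The concern.** Safety is half of the stated objective (section 3). The protocol identifies the gut as the place where the product meets the body, yet the reactions it names are systemic, haematological or allergic. A mild, short-lived bowel upset is easily missed when nobody asks about it in set words. It may also be picked up at one centre and not at another, and 10.2.6 treats the trial as multi-centre.

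Two things would suffer. First, the reported frequency of gastrointestinal reactions would depend partly on how each investigator happened to enquire. Second, bowel symptoms that subjects already had would be hard to set apart from new ones, because no symptom record before dosing is specified. The second matters most if the trial is single-arm, as 4.1 states, since D0 is then the only within-trial comparator.

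**Working it through.** No arithmetic beyond a count applies. The plan states no sample size, expected reaction rate or detection figure, so there is nothing to reproduce. The check sets the safety sections side by side.

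**1. What is named.** Section 7.2.2 gives fever and chills (2), coagulation dysfunction and allergy (2), and disability (1). That is 2 + 2 + 1 = 5 named items, of which 0 are gastrointestinal. Sections 7.3, 7.4, 7.4.1 and 8.1 to 8.5 name no gastrointestinal symptom either. The laboratory panel in 7.3 covers blood, urine, liver and kidney, and has no gut-specific item. The gastrointestinal tract appears only in the Introduction, as the route of exposure and of antigen presentation.

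**2. What is nevertheless in scope.** The 7.2.2 items are introduced as examples. Section 7.3 grades any discomfort, 7.4 repeats all trial indicators at each follow-up visit, and 8.1 takes in every adverse event. A subject with diarrhoea who tells the investigator should therefore be recorded.

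**3. How it would be found.** The documents do not say how symptoms are elicited: there is no fixed question, list or recall period. The only symptoms an investigator is told by name to look for are the five above. The diary card could capture symptoms day by day, but as described it does not.

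**4. When it would be found.** Subjects are outpatients (5.1) and the scheduled visits are 7 days apart. Section 7.4 also refers to daily clinical examinations, but no daily visit is scheduled and nothing says how outpatients would be examined daily. If those examinations do not take place for outpatients, a symptom on the first or second day is reached only by recall at D7. These two statements in 7.4 should be reconciled.

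**5. What it would be compared with.** Section 7.4.1 provides history and physical examination at D0 but no graded symptom record to match those at D7 to D28. Section 10.2.6 defines change from before to after for laboratory values only. Sections 4.1 and Summary 4 describe one arm, while 6.3 and 10.2.3 refer to a control group. Under the single-arm reading there is no concurrent rate of ordinary bowel symptoms to set against the observed one.

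**6. Link to the main efficacy indicator.** Immunogenicity is the main indicator (7.1). No section asks for vomiting after the capsule or its time, so the analysis could not identify subjects in whom retention of the dose is in doubt. Section 4.2 describes a single administration, and 6.3 a daily one. That contradiction needs reconciling in its own right, and it also determines how many administrations a vomiting record would cover.

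**The case against.** The strongest reply is that gut reactions are already collected. The 7.2.2 list is illustrative, 7.3 puts recording in the investigator's hands on a scale that includes a no-symptoms level, 7.4 calls for recording at daily examinations, and 8.1 excludes nothing. All of that stands. It rules out several stronger readings that a reader might draw:

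- **That gut reactions are recorded only if the subject volunteers them, or are left to chance.** The text does not say this. A scale with a no-symptoms level suggests that every subject is assessed. The method of enquiry is simply unspecified.
- **That old and new bowel symptoms cannot be told apart.** Medical history is taken at D0 and may help. The supportable statement is that no D0 symptom record is specified for the purpose.
- **That the reported reaction rate will be too low by some stated amount.** That would need a true rate and a capture fraction, and the documents give neither.
- **That a vomited dose would be read as non-response.** This is possible but conjectural, since vomiting is a recordable event under 8.1.
- **That the product is a live organism in the protocol's own terms.** The Introduction calls the spores dormant, and the point does not depend on this.

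It is also fair to say that the case report form, whose side-effect table is mentioned in 8.2, is not among the documents. It may prompt by body system. If it does, part of the gap is closed in practice, though not in the protocol.

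What survives is the difference between an event being in scope and every subject being asked about it in the same way. None of the provisions cited supplies a uniform question or a symptom baseline.

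**Conclusion.** The point holds as a cheap improvement to data collection. It does not show that safety data are absent or invalid. No gastrointestinal symptom is named for observation, although the protocol places the product's action at the gastrointestinal mucosa. Capture rests on general items with no uniform question, no symptom diary and no D0 symptom record. Mild gastrointestinal reactions may therefore be under-ascertained or collected unevenly, and pre-existing bowel symptoms lack a specified baseline.

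The size is not calculable from the documents. The conclusion assumes that the unseen case report form does not already contain a gastrointestinal prompt, and it weighs more if the single-arm description in 4.1 is the operative one.

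**What to change.** 1. In 7.2.2, add nausea, vomiting, diarrhoea, abdominal pain or bloating, and constipation to the named symptoms.
2. Ask about them with the same fixed question at D0 before dosing (add to 7.4.1) and at D7, D14, D21 and D28.
3. Add these symptoms to the diary card already provided for in 11.1, with the time of any vomiting after the capsule, so that early symptoms do not rest on recall at D7.
4. In 10.2.6, tabulate symptoms that are new or worse than at D0, by visit.

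**Cost.** A few more entries on the case report form and diary card, at visits already planned. No added visit or laboratory test is needed. Reported reaction rates may look slightly less favourable than under general enquiry. The change has to be made before dosing starts, because a pre-dose symptom record cannot be obtained afterwards.
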